The programmed death receptor-1 (PD-1) physiologically acts as an immune checkpoint receptor, enabling self-tolerance by T-cells in normal tissue. Unbound PD-1 allows the normal immune response by T cells to occur. Binding of PD-1 to the ligands PD-L1 and PD-L2 suppresses the immune response. Abnormal PD-L1 expression on tumor cells leads to activation of PD-1 and suppression of cytotoxic T-cell activity. The T-cell tolerance allows the tumour cells to avoid recognition and elimination by the immune system (1). In September 2014 Pembrolizumab, a humanized monoclonal immunoglobulin G4 kappa antibody against PD-1, was approved in the United States of America for the treatment of incurable melanoma in patients with disease progression following first line treatment. Anti-PD-1 therapies may be a novel therapeutic option in the treatment strategy of advanced non-small cell lung cancer (NSCLC). Data from the KEYNOTE-001 study showed that NSCLC patients with detectable PD-L1 expression had a response under treatment with Pembrolizumab (2). Positive results could be demonstrated in treatment-naïve as well as in previously treated advanced NSCLC. There is probably a correlation between tumor PD-L1 expression and improved pembrolizumab antitumor activity (3). In March 2015 Nivolumab, a humanized monoclonal immunoglobulin G4 kappa antibody against PD-1, was approved in the United States of America for the treatment of incurable NSCLC. The approval was reached after the publication of the CHECKMATE-017 trial, where a benefit in overall survival of 3.2 months could be demonstrated in comparison to docetaxel in subjects after standard platinum-based chemotherapy with following tumor progression (4). In the CHECKMATE-063 trial under Nivolumab a response could be achieved in 15% of subjects after at least two lines of standard chemotherapy (5). In May 2015 a positive CHMP opinion was published by the EMA.

Lung cancer is the second most common cancer and is the primary cause of cancer-related death in both men and women in the United States (6). Currently, 80% of patients with lung cancer are given a diagnosis of primary NSCLC. Malignant pleural effusion (MPE) is a common complication of advanced lung cancer. The presence of MPE indicates a poorer prognosis for patients with lung cancer and impairs their quality of life. Pleural effusion is a convenient clinical sample with important clinical diagnostic significance. It may be an alternative source supplying useful information about the neoplasm's biology in terms of molecular genetic and immunopathologic profile.

2. Objectives

This is a prospective diagnostic pilot study to create hypotheses regarding immunocytochemistry (ICC) PD-L1 analysis of pleural effusions in NSCLC patients as compared to the reference standard of PD-L1 immunohistochemistry (IHC). This comparison will be done to assess sensitivity and specificity of PD-L1 detection by ICC in pleural effusions.

The main hypothesis is, that ICC analysis of PD-L1 from pleural effusion has a relevant diagnostic value with a specificity of ~90% as compared to the immunohistochemical reference standard.

3. Outcome

3.1. Primary Outcome Measures

- Number/prevalence of PD-L1-positive patients according to immunohistochemistry (IHC) of pleural biopsy
- Number/prevalence of PD-L1-positive patients according to immunocytochemistry (ICC) of pleural aspirate

3.2. Secondary Endpoints

- IHC results of different bronchoscopic samples

4. Study Population

The population for selection of potential study participants is comprised of clinical routine patients presenting with (suspected malignant) pleural effusion. These patients must have an indication for pleural puncture. The cause and nature of the pleural effusion (e.g. presence of non-small cell lung cancer, NSCLC) at this time point will be unknown in many cases. To establish this, further routine diagnostic procedures are required. While patients will be included before the planned routine examinations and thus before presence of NSCLC can be confirmed, only patients with confirmed diagnosis of non-small cell lung cancer will be included in the data analysis.

A patient in whom suspicion of pleural manifestation of lung cancer is not confirmed, will be considered a screening failure and thus excluded from the study.

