4.2. Exclusion Criteria

- Age $<$ 18 years
- Pregnancy and/or lactation
- Acute and life-threatening illness (unstable angina pectoris, acute pulmonary arterial embolism, myocardial infarction, etc.)

- Any contraindication to undergo thoracoscopy (e.g. anticoagulation therapy which cannot be discontinued for the procedure)
- Any medical, psychological or other condition impairing the patient's ability to provide informed consent
- Exclusion of non-small cell lung cancer as cause of pleural effusion after clinical routine examinations leads to study exclusion of patient

5. Study Plan and Assessments

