5.1. Selection of Patients

Patients presenting within clinical routine with pleural effusion and suspected or known underlying lung cancer and who satisfy the in- and exclusion criteria as far as they can be assessed at that time, are considered for study participation.

These patients will be informed about all routine clinical examinations and assessments before informed consent will be obtained. However, informed consent for study participation will be obtained before (routine) pleural puncture to ensure that patients agree with the study-specific additional diagnostic analysis of the collected pleural effusion material.

All invasive procedures described herein are part of the patient's clinical routine treatment to achieve a clinical diagnosis. The routine examinations and study-associated data collection for each patient are outlined below. The individual patient's study participation will be concluded, once all of these steps are completed.

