5.6. Immunocytochemistry (ICC) and Immunohistochemistry (IHC)

The pleural fluid obtained by pleural puncture will be in part used for standard clinical routine analysis and another part will be subject to study-specific PD-L1 analysis. The same applies to the histological samples obtained by thoracoscopy and potential bronchoscopy. These analyses will reveal nature and cause of the pleural effusion. In case the corresponding results confirm an NSCLC diagnosis, all results from ICC and IHC will be collected for analysis within the study. Should the results rule out NSCLC, the patient will be considered a screening failure and excluded from the study.

For PD-L1 analysis in both ICC and IHC, the PD-L1 IHC 22C3 pharmDx Kit (Dako) will be used.

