5.7. Documentation of Adverse Events

All adverse events occurring during each patient's actual study participation will be assessed for diagnostic procedure relatedness. Procedure-related adverse events will be documented for later study-specific analysis.

6. Statistical Analysis

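### Read literally, the confirmed-NSCLC rule in section 4 leaves procedure-related adverse events in exposed screening failures out of the analysis that section 5.7 promises; section 5.7 names no analysis set (minor).

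*Combined protocol and SAP*

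**What the plan says.** All references are to the combined protocol and SAP.

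- **Consent and exposure.** Section 5.1: "informed consent for study participation will be obtained before (routine) pleural puncture". Puncture (5.3), thoracoscopic pleural biopsy (5.4) and, in some patients, bronchoscopic biopsy (5.5) follow.
- **Diagnosis.** Section 5.6 says of the work on the fluid and biopsy samples: "These analyses will reveal nature and cause of the pleural effusion".
- **Exclusion.** Under section 4, a patient whose suspected pleural lung cancer is not confirmed "will be considered a screening failure and thus excluded from the study". Section 4.2 lists as an exclusion criterion: "Exclusion of non-small cell lung cancer as cause of pleural effusion after clinical routine examinations leads to study exclusion of patient". Section 5.6 agrees: "Should the results rule out NSCLC, the patient will be considered a screening failure and excluded from the study".
- **Analysis population.** Section 4: "only patients with confirmed diagnosis of non-small cell lung cancer will be included in the data analysis". This is the only analysis-population rule in the document.
- **Adverse events.** Section 5.7 has every event during a patient's participation assessed for relation to the diagnostic procedures, and adds: "Procedure-related adverse events will be documented for later study-specific analysis". It names no analysis set.
- **Planned analyses.** Section 6 describes no adverse-event analysis, and section 3 lists no safety outcome.

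**The concern.** The restriction to confirmed NSCLC suits the comparison of ICC with IHC, because the diagnostic question concerns NSCLC patients. It does not suit procedure complications. Every consented patient who is punctured or biopsied is exposed to them, whatever the histology later shows.

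In many patients membership of the analysis is settled by a result obtained after that exposure. If the section 4 rule is applied to adverse events as written, a complication in a patient whose effusion proves to have another cause is recorded and then left out of the summary. Two analysts could also read sections 4 and 5.7 differently and report different event counts from the same data.

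At stake are the completeness of the adverse-event summary and, if risk differs between confirmed and unconfirmed patients, its accuracy. The diagnostic accuracy results are not at stake.

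**Working it through.** **1. The plan's own figures.** The plan gives no complication rate, safety denominator or screening-failure fraction, so there is no safety figure to reproduce. Its one calculated figure, the sample size in section 7, reproduces with W = 0.10 entered as printed: 1.96² × 0.90 × 0.10 / 0.10² = 34.57, and 34.57 / 0.75 = 46.1, against the stated 46. This point does not change it.

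**2. The sections in sequence.**

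| Step | Section | Status of a patient who turns out not to have NSCLC |
|---|---|---|
| Consent | 5.1 | In the study |
| Puncture, thoracoscopy, possibly bronchoscopy | 5.3–5.5 | In the study and exposed |
| Events assessed and documented | 5.7 | Covered; no NSCLC restriction stated |
| Diagnosis from samples | 5.6 | Screening failure, excluded |
| Data analysis | 4 | Not included |
| Adverse-event analysis | 5.7 | Not stated; the section 4 rule is the only one available |

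The gap is in the last row. Section 5.7 secures the recording of the event, but nothing secures its analysis.

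**3. How many patients could be left out.** Let f be the share of consented, exposed patients who are confirmed. The documents do not give f; 0.8, 0.6 and 0.4 are assumed. The share left out is 1 − f. Section 7 does not say whether its total of 50 counts confirmed or consented patients, so both readings are shown.

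| f | Share left out | Left out if 50 are confirmed: 50/f − 50 | Left out if 50 are consented: 50(1 − f) |
|---|---|---|---|
| 0.8 | 20% | 12.5 | 10 |
| 0.6 | 40% | 33.3 | 20 |
| 0.4 | 60% | 75 | 30 |

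**4. Information lost.** With zero events in n patients, the one-sided 95% upper bound on the complication risk is 1 − 0.05^(1/n). For n = 50 it is 5.8%. If those 50 are the confirmed patients, all exposed patients number about 62, 83 and 125 for the three values of f, and the bounds are 4.7%, 3.5% and 2.4%. These figures show precision, not bias.

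**5. Bias.** With risk p_c in confirmed and p_u in unconfirmed patients, the restricted summary estimates p_c. The rate in all exposed patients is f·p_c + (1 − f)·p_u. The risks below are assumed.

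| p_c | p_u | Restricted | All exposed, f = 0.8 / 0.6 / 0.4 |
|---|---|---|---|
| 5% | 5% | 5% | 5% / 5% / 5% |
| 5% | 10% | 5% | 6% / 7% / 8% |
| 10% | 5% | 10% | 9% / 8% / 7% |

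For example, with f = 0.6 in the second row: 0.6 × 5% + 0.4 × 10% = 7%. Under equal risk, 20%, 40% or 60% of events are lost but the rate is unbiased. Otherwise the restricted figure can be too low or too high. The documents give no risks by diagnosis, so they do not settle the direction.

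**The case against.** The case on the other side has several parts.

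- **No passage applies the section 4 rule to adverse events.** Section 5.7 has its own scope, all events during participation, without an NSCLC restriction. Participation starts before puncture, so these events are documented. This stands as far as documentation goes. It does not settle analysis, where section 4 is unqualified and section 5.7 is silent on the set.
- **No complication rate is planned.** This stands: there is no defined estimate to call biased. But section 5.7 does promise an analysis of the events, and that analysis needs a population.
- **The procedures are routine and the study is a hypothesis-generating pilot.** Section 5.1 says: "All invasive procedures described herein are part of the patient's clinical routine treatment to achieve a clinical diagnosis". This stands, and it limits the severity.
- **Not every diagnosis depends on these samples.** Section 5.1 admits patients with known lung cancer, and section 4 says the cause is unknown in many cases, not all. This stands; the point concerns the remainder.

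A reader might infer more: that complications are under-reported because a complication that stops the biopsy also stops confirmation of NSCLC, which would push the rate down. The documents do not support that as a general claim. Section 5.4 provides for surgical thoracoscopy where the internistic route is not feasible. Section 5.5 points to bronchoscopic samples, particularly where none can be had from the pleura, and section 5.6 also sends pleural fluid for routine analysis. A failed pleural biopsy therefore need not leave NSCLC unconfirmed. Sections 4.2 and 5.6 exclude patients when NSCLC is ruled out, which an abandoned biopsy does not do; only section 4 excludes for lack of confirmation. The mechanism is possible in single patients, but its size is unknown.

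**Conclusion.** The point holds as a minor one. Section 4 restricts the data analysis to confirmed NSCLC without exception and removes the other patients after they have been exposed. Section 5.7 promises an analysis of procedure-related events without saying in whom. Followed literally, the plan leaves documented events in exposed screening failures out of that analysis.

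The loss of information follows directly from that reading. Its extent depends on the unstated screening-failure fraction: 20% to 60% of exposed patients over the assumed range. Bias is possible but conditional on risk differing by diagnosis, and it could go either way. A claim that the plan's complication rate is biased downward would go beyond the documents, because they define no such rate and give no risks by diagnosis.

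Sensitivity, specificity and the sample size are unaffected. Safety is not a listed outcome and the procedures are clinical routine, so no stated conclusion of the study depends on this.

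**What to change.** - **Section 4:** limit the confirmed-NSCLC restriction to the ICC and IHC analyses.
- **Section 5.7:** state that procedure-related adverse events are summarised for all consented patients who undergo pleural puncture, thoracoscopy or bronchoscopy, whatever the final diagnosis and including screening failures, with the confirmed-NSCLC subset shown separately.

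The change needs no further procedure, visit or patient and leaves the primary analysis as it is. Its cost is a wording change in two sections and a minimal adverse-event record kept for screening failures, who have already consented.

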4.1. Inclusion Criteria

- Age \geq 18 years
- Presence of malignant pleural effusion with indication for pleural puncture and thoracoscopy
- Confirmed diagnosis of non-small cell lung cancer according to ERS guidelines (to be confirmed after study inclusion when results from routine clinical examinations are available)
- Written informed consent

4.2. Exclusion Criteria

- Age $<$ 18 years
- Pregnancy and/or lactation
- Acute and life-threatening illness (unstable angina pectoris, acute pulmonary arterial embolism, myocardial infarction, etc.)

- Any contraindication to undergo thoracoscopy (e.g. anticoagulation therapy which cannot be discontinued for the procedure)
- Any medical, psychological or other condition impairing the patient's ability to provide informed consent
- Exclusion of non-small cell lung cancer as cause of pleural effusion after clinical routine examinations leads to study exclusion of patient

5. Study Plan and Assessments

5.1. Selection of Patients

Patients presenting within clinical routine with pleural effusion and suspected or known underlying lung cancer and who satisfy the in- and exclusion criteria as far as they can be assessed at that time, are considered for study participation.

These patients will be informed about all routine clinical examinations and assessments before informed consent will be obtained. However, informed consent for study participation will be obtained before (routine) pleural puncture to ensure that patients agree with the study-specific additional diagnostic analysis of the collected pleural effusion material.

All invasive procedures described herein are part of the patient's clinical routine treatment to achieve a clinical diagnosis. The routine examinations and study-associated data collection for each patient are outlined below. The individual patient's study participation will be concluded, once all of these steps are completed.

5.2. Anthropometry, Vital Signs, Medical History, Medication

The following data will be collected for analysis within the study:

1. Anthropometric data (age, gender, height, weight, BMI)
2. Office blood pressure according to ESH/ESC guidelines
3. Current medication
4. Medical history incl. any oncological pre-medication
5. Smoking history

5.3. Pleural puncture (non-study specific routine examination)

The pleural effusion will be treated and diagnosed by puncturing of the pleural cavity at the location of effusion. During this process the excess pleural fluid will be removed/collected and used for later analysis by an external pathology department.

5.4. Thoracoscopic pleural biopsy (non-study specific routine examination)

After pleural puncture, histological pleura samples will be obtained by pleural biopsy, primarily applying internistic thoracoscopy. If internistic thoracoscopy is not feasible (e.g. due to distinct intergrowth), the patient will undergo surgical thoracoscopy. In either case, at least five biopsies will be taken.

5.5. Optional bronchoscopic lung biopsy (non-study specific routine examination)

In some cases, suspicious tumor masses within the lung and/or intrathoracic lymph nodes are detected by preceding radiologic assessment and routinely sampled for further histological analyses. This applies in particular when no histological samples can be obtained from the pleura. In these cases, the corresponding results will also be considered for study-associated analysis.

5.6. Immunocytochemistry (ICC) and Immunohistochemistry (IHC)

The pleural fluid obtained by pleural puncture will be in part used for standard clinical routine analysis and another part will be subject to study-specific PD-L1 analysis. The same applies to the histological samples obtained by thoracoscopy and potential bronchoscopy. These analyses will reveal nature and cause of the pleural effusion. In case the corresponding results confirm an NSCLC diagnosis, all results from ICC and IHC will be collected for analysis within the study. Should the results rule out NSCLC, the patient will be considered a screening failure and excluded from the study.

For PD-L1 analysis in both ICC and IHC, the PD-L1 IHC 22C3 pharmDx Kit (Dako) will be used.

5.7. Documentation of Adverse Events

All adverse events occurring during each patient's actual study participation will be assessed for diagnostic procedure relatedness. Procedure-related adverse events will be documented for later study-specific analysis.

6. Statistical Analysis

6.1. Primary Analysis

The main hypothesis is, that ICC analysis of PD-L1 from pleural effusion has a relevant diagnostic value with a specificity of ~90% as compared to the immunohistochemical reference standard. To test this hypothesis, the number of PD-L1 positive and negative detections for each sample type will be documented and used for calculation of sensitivity and specificity. Furthermore, the frequency with 95% confidence interval of PD-L1 positive patients according to ICC of pleural fluid will be calculated.

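### Do fluids that cannot be scored for PD-L1 put the primary ICC results in section 6.1 on two different denominators?

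*Combined protocol and SAP*

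**What the plan says.** The two primary outcomes in section 3.1 are worded alike: "Number/prevalence of PD-L1-positive patients according to immunohistochemistry (IHC) of pleural biopsy" and "Number/prevalence of PD-L1-positive patients according to immunocytochemistry (ICC) of pleural aspirate". Neither has a stated denominator.

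Section 6.1 describes two calculations. For accuracy, "the number of PD-L1 positive and negative detections for each sample type will be documented and used for calculation of sensitivity and specificity". For prevalence, "the frequency with 95% confidence interval of PD-L1 positive patients according to ICC of pleural fluid will be calculated".

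Section 4 says who enters the analysis: "only patients with confirmed diagnosis of non-small cell lung cancer will be included in the data analysis". It sets no condition on having an ICC result.

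On material, section 5.3 says that "the excess pleural fluid will be removed/collected and used for later analysis by an external pathology department". Section 5.6 says the fluid "will be in part used for standard clinical routine analysis and another part will be subject to study-specific PD-L1 analysis", and applies the same split to the histological samples. It then provides that "In case the corresponding results confirm an NSCLC diagnosis, all results from ICC and IHC will be collected for analysis within the study". No section mentions a sample that cannot be scored.

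**The concern.** A patient may have NSCLC confirmed on pleural biopsy while the fluid sent for PD-L1 yields no result. That patient is in the section 4 analysis population. The fluid is neither a positive nor a negative detection, so it seems to leave the sensitivity and specificity table. If the ICC-positive frequency is taken over all confirmed patients, the same fluid stays in that denominator and in effect counts as not positive.

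Three consequences would follow:

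- The ICC prevalence would fall by the unscorable share, while the 2x2 table would not move.
- Lost fluids could offset false positives, so the two primary prevalences would agree although ICC misclassified 10% of IHC-negative patients.
- The share of unscorable fluids bears on feasibility, which section 7 gives as a purpose of the study, and no planned output is devoted to it.

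The plan offers some grounds for expecting such fluids. Only part of the fluid goes to PD-L1 analysis and no minimum amount is set, whereas section 5.4 requires at least five biopsies for the reference.

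**Working it through.** **1. Reading the text.** In the frequency sentence of 6.1, the word for patients describes who is counted as positive, that is, the numerator. No denominator is given there or in 3.1. Section 4 states a necessary condition for entering the analysis. It does not say that every confirmed patient enters every denominator. Two readings therefore fit: all confirmed NSCLC patients, or those with an ICC result. Under the second, the frequency and the accuracy table treat an unscorable fluid in the same way.

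**2. The plan's own sample size.** Inputs from section 7: z = 1.96, SP = 0.90, W = 0.10, P = 0.25.

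- IHC-negatives needed: 1.96² × 0.90 × 0.10 / 0.10² = 34.57
- Patients: 34.57 / 0.75 = 46.10, stated as 46
- With 10% drop-out: 46 × 1.1 = 50.6, or 46 / 0.9 = 51.1, stated as 50

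The figures reproduce to within about one patient and do not depend on the denominator question.

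**3. Size of the denominator choice.** The sensitivity SE and the unscorable share u are not in the documents. Assume SE = 80%, u = 10% to 30%, with u independent of PD-L1 status. The expected ICC-positive frequency among scorable fluids is

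f = P × SE + (1 − P)(1 − SP) = 0.25 × 0.80 + 0.75 × 0.10 = 27.5%.

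Over all patients it is (1 − u) × f = 24.8%, 22.0% and 19.3% at u = 10%, 20% and 30%. In whole patients, with N = 50 and exact 95% intervals:

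| u | Scorable fluids | All patients | Shift (points) |
|---|---|---|---|
| 10% | 12/45 = 26.7% (14.6–41.9) | 12/50 = 24.0% (13.1–38.2) | 2.7 |
| 20% | 11/40 = 27.5% (14.6–43.9) | 11/50 = 22.0% (11.5–36.0) | 5.5 |
| 30% | 10/35 = 28.6% (14.6–46.3) | 10/50 = 20.0% (10.0–33.7) | 8.6 |

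The half-lengths of these intervals run from (33.7 − 10.0)/2 = 11.9 to (46.3 − 14.6)/2 = 15.9 points. In every row the shift is smaller than either half-length. The number of positives, which 3.1 also names as an outcome, is the same under both readings.

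**4. Specificity.** With unscorable fluids excluded it stays at 90%. Counted as negative it becomes u + (1 − u) × 0.90 = 91%, 92% and 93%. Excluding them leaves 50 × 0.75 × (1 − u) = 33.75, 30 and 26.25 IHC-negatives, and half-widths 1.96 × √(0.09/n) of 10.1, 10.7 and 11.5 points. The plan's W is 10 points, and 50 patients with none lost would give 9.6.

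**5. Offsetting false positives.** The two prevalences agree when (1 − u) × f = 25%, so u = 1 − 0.25/f. This gives u = 9%, 17% and 23% at SE = 80%, 90% and 100%. At SE = 70%, f = 0.25 × 0.70 + 0.075 = 25.0%, so they agree at u = 0. Two marginal frequencies can match despite 10% false positives with no fluid lost at all. Section 6.1 calculates specificity directly, so those false positives show in any case.

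**6. Recovering the unscorable count.** Section 6.1 documents positive and negative detections for each sample type. Taking one ICC result per patient, 50 confirmed patients with 11 positive and 29 negative fluids leave 50 − 40 = 10 without a result. Either frequency can be computed from those counts.

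**The case for a change.** The strongest case for a change is that collecting results does not define a denominator, and that one chosen after the results are seen could be the more flattering one. The handling rule also matters for sensitivity. If unscorable fluids were counted as negative, the assumed 80% would fall to 0.80 × (1 − u) = 72%, 64% and 56%, far more than specificity moves. The 10% drop-out allowance in section 7 is not said to cover such samples, and a feasibility pilot ought to show how often the fluid can be read.

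Part of this stands. The plan has no rule for a non-evaluable sample, and stating one would be good practice. But nothing in 6.1 directs that an unscorable fluid be counted as negative. The fall in sensitivity belongs to a rule the plan does not contain, and sensitivity is imprecise here anyway: with about 12 IHC-positives expected (50 × 0.25 = 12.5), 10 of 12 gives 83.3% with an exact interval of 51.6% to 97.9%. There is no decision rule for a favourable denominator to exploit, and the documented counts expose either choice.

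The evidence that fluids in particular will fail is also thin. Section 5.6 splits the histological samples in the same way, and the one sampling failure the plan foresees (section 5.5) is absent pleural histology, on the reference side. The denominator question therefore applies to IHC as much as to ICC.

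**Conclusion.** The concern does not call for a change. Section 6.1 contains no written conflict between two denominators. It leaves one unstated, together with the handling of non-evaluable ICC or IHC samples. Analysts would sensibly use the evaluable samples for each result and say how many were not evaluable, a number they can get by subtraction.

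Under the assumptions used (50 patients, sensitivity 80%, 10% to 30% of fluids unscorable independently of PD-L1 status, and the plan's specificity of 90% and prevalence of 25%), the choice moves the ICC-positive frequency by about 3 to 9 points, within the confidence half-width. Specificity, on which the main hypothesis and the sample size rest, moves by 1 to 3 points. If no fluid is unscorable, the two denominators coincide. In a hypothesis-generating pilot, a non-evaluable category and an extra sensitivity analysis would be additions to the report. They would correct no stated rule or figure.
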